Clinical Study Protocol: MVT-601-035 Effective: 13-August-2018

Abbreviations: BP, blood pressure; ECG, electrocardiogram; HR, heart rate; PGA, Patient Global Assessment; SF-36, Short Form (36) Health Questionnaire; UFS-QoL, Uterine Fibroid Symptom and Health-Related Quality of Life; WPAI-UF, Work Productivity Activity Index-Uterine Fibroid

The Week 104 visit should occur on or after the 2-year anniversary of Study Day 1 of the Parent study.

- ^c The Safety Follow-up visit may be waived if the patient enrolls directly into another relugolix clinical study upon completion of the Week 104 visit.
- d May be signed up to 30 days prior to the Week 52/Baseline visit or during the Week 52/Baseline visit. Enrollment in MVT-601-035 is defined by administration of the first dose of MVT-601-035 study drug.
- e Record all prescription and nonprescription drug and supplements taken from the Week 52/Baseline visit through the Safety Follow-up period.
- This is an MVT-601-3003 (OLE study) Week 52 procedure that serves as the Week 52/Baseline procedure for MVT-601-035 and is covered under the informed consent for the OLE study.
- The indicated procedure may be performed at the unscheduled visit based on the purpose of the visit (e.g., follow-up for an adverse event or abnormal laboratory test).
- h The exam may include a gynecologic examination, if indicated based on signs and symptoms.
- The 12-lead ECG will be submitted for central reading at the Week 52/Baseline visit. Any subsequent ECGs performed at investigator discretion will be read locally.
- Clinical laboratory tests required include clinical chemistries and a complete blood count. At the Week 52/Baseline visit and Week 104 visit, additional tests include: fasting (at least 8 hours) glucose, lipid profile, and hemoglobin A1c.
- k Pre-dose specimen drawn at Week 56 only.
- 1 Specimen for FSH will be collected on patients who have been amenorrhoeic (i.e., those who have not required the use of any feminine products) since randomization.

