2.2. Sample Size Considerations

Because this is an extension of study MVT-601-3003, the sample size of this study was based on approximately the number of patients who completed a pivotal study (n = 780 patients in total), and who participated in the LTE study (n = 600 patients in total assuming about 20% dropout rate at 6 months from the pivotal studies). Assuming the proportion of responders at Week 52 in MVT-601-3003 LTE study is 60%, it was estimated that approximately 360 patients were to be randomized into this study.

With 360 patients, the study would have at least 90% power to detect a difference of 20% or greater between relugolix+ E2/NETA group and placebo group for the primary endpoint. The following assumptions were used to determine the sample size for this study:

- 2-sided type I error rate: 0.05
- Randomization: 1:1
- Responder rate for placebo group: 40%
- Responder rate for relugolix + E2/NETA group: 60%
- Dropout rate: 20%

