Step B: If the stratified test statistics cannot be calculated due to event having not occurred in certain stratum, unstratified test will be used instead.

Step C: If unstratified test is still not estimable, the stratified version of the Mantel-Haenszel test using pooled KM estimators in each stratum will be constructed as the following. This test statistics follows a chi-square distribution with one-degree freedom.

$$\chi_{MH}^2 = \frac{\left\{ \sum_{s=1}^M \frac{n_{R_s} n_{P_s}}{n_{R_s} + n_{P_s}} (\widehat{S}_{R_s}(t) - \widehat{S}_{P_s}(t)) \right\}^2}{\sum_{s=1}^M n_{R_s} n_{P_s} V(\widehat{S}_{pooled_s}(t))}$$

It is noted that sustained responder rate at Week 104 (Day 365) as a key secondary endpoint will be defined as the KM estimates from the same KM curves and will be analyzed using the same method as described above.

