7.3.1.2. Censoring Rules

The censoring rules in the Kaplan-Meier method are described as the following (see Table 8):

- For patients with relapse (MBL volume ≥ 80 mL) during the randomized treatment period, they will be considered as having an event at the time of first relapse. The time of first relapse is the date of the earliest menstrual bleeding days within the first FP collection visit window in which the MBL volume is ≥ 80 mL.
- For patients who did not have relapse during the randomized treatment period and had complete FP collection at each scheduled visit during the randomized treatment period,

they will be considered as not having an event and will be censored at the last available FP collection visit date during the randomized treatment period.

- For patients who did not have relapse during the randomized treatment period and had incomplete or missing FP collection during the randomized treatment period, they will be considered as censored using the following censoring rules:
 - If patients did not have FP collection after Week 64 (ie, have up to 3 FP collection visits through Week 64), they will be censored at the date of the last available FP collection visit if there are no consecutive visits with incomplete or missing FP collection; they will be censored at the date of the last available FP collection visit prior to the consecutive visits with incomplete or missing FP collections if there are two or more consecutive visits with incomplete or missing FP collections.
 - If patients had FP collection after Week 64
 - did not have incomplete or missing FP collections at consecutive visits, they will be censored at the last available FP collection date during the randomized treatment period.
 - had two or more consecutive visits with incomplete or missing FP collections, they will be censored at the last available FP collection visit date prior to the two consecutive visits during the randomized treatment period.

The time to event or censoring will be summarized by the Kaplan-Meier method. If the event time or censoring time is after the target (Day 365), Day 365 will be used as the event time or censoring time.

A sensitivity analysis will be performed considering different censoring rules (see Section [7.3.4.3](#)).

Table 8: Censoring Rules for Kaplan-Meier Analysis During Randomized Treatment Period

Type of Patients	Event	Event Time ^a	Censored	Censoring Time ^a

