7.3.2.3. Feminine Product Collection Interval

The FP collection interval at each visit is driven by types of bleeding patterns experienced by the patients, as described below:

- For patients who continue to have cyclic bleeding, the length of the interval depends on the duration of the patient's natural cycle;
- Patients who report irregular, non-cyclic bleeding are instructed to collect and return all FP used between study visits, up to 35 days, as per the schedule of events;
- For patients who report amenorrhea on the Feminine Product Collection eCRF page, an interval of last 35 days of treatment will be reviewed to ensure that reported amenorrhea is not due to incomplete collection.

For patients who are in the midst of an episode of cyclic bleeding at the time of the FP collection visit (or the last visit in the randomized treatment period which is prior to Week 104), the visit window may be extended up to 7 days after Week 104 visit (or last visit) to ensure patients return all used FPs over that bleeding episode.

Per protocol, all used FPs are to be collected at each visit and returned for analysis using the alkaline hematin method. For patients who continue to have menstrual bleeding, study visits are timed such that the FPs used in the entire menstrual bleeding cycle are collected in one container provided at each visit.

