7.4.1.1. Time to Relapse (Menstrual Blood Loss Volume \geq 80 mL)

For the endpoint of time to MBL volume \geq 80 mL (event) during the randomized treatment period, time-to-event will be defined as weeks from first dose of the randomized withdrawal study drug to first occurrence of MBL volume of \geq 80 mL. The corresponding menstruation start date will be considered as the event date. Patients without an event will be censored by following the same censoring rules described in Section 7.3.1.2. Kaplan-Meier methods will be used to describe the time to event (relapse) distributions for each study treatment group from which median time to event will be derived. Hazard ratio (95%CI) of relugolix + E2/NETA to placebo for risk of relapse (MBL volume \geq 80mL) will be provided using a proportional hazard model stratified by the stratification factors (pivotal study baseline MBL volume (< 225 ml vs. \geq 225 mL) and duration of exposure to relugolix (28 weeks vs. 52 weeks). p-value for comparison of relugolix + E2/NETA to placebo based on the stratified log-rank test will be provided.

7.4.1.2. Proportion of Patients Who Maintained a Menstrual Blood Loss Volume of < 80 mL at Week 104

The proportion of patients who maintained a menstrual blood loss volume of < 80 mL by Week 104 (52 weeks of the randomized treatment period) as measured by the alkaline hematin method will be analyzed using the same method as that for primary efficacy endpoint described in Section 7.3. It is noted that sustained responder rate at Week 104 (Day 365) will be defined as the KM estimates from the same KM curves and will be analyzed using the same method as for the primary endpoint (see Section 7.3.1).

No subgroup analysis will be performed for this secondary efficacy endpoint.

The proportion of patients who maintained a menstrual blood loss volume of < 80 mL will also be summarized during the cumulative treatment period (including both randomized treatment period and the retreatment period).

The proportion of patients who had a menstrual blood loss volume of < 80 mL at a visit will also be summarized descriptively by visit during the cumulative treatment period (including both randomized treatment period and the retreatment period).

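### SAP 7.3.1.2 keeps relapses that begin after Day 365 as events at Day 365, so the Week 104 sustained responder rate counts failures from beyond its own horizon

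*SAP*

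**What the plan says.** The sustained responder rate is a Kaplan-Meier estimate of staying below 80 mL, read at Day 169 for the primary endpoint (SAP 7.3.1). SAP 7.3.1.1 says that the Week 104 (Day 365) rate "will be defined as the KM estimates from the same KM curves". It is the second of three key secondary endpoints in the fixed sequence of SAP 7.4.1, after time to relapse.

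At the end of follow-up, SAP 7.3.1.2 provides that for later times "Day 365 will be used as the event time or censoring time". Nothing there changes a late relapse from event to censored.

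Time runs from the first dose of randomized drug (SAP Table 8, footnote), taken the morning after the Week 52/Baseline visit (SAP 2.1). The last visit is tied to a different origin. Protocol 1.1 states: "The Week 104 visit should occur on or after the 2-year anniversary of Study Day 1 of the Parent study". The schedule gives this visit a +10-day window, and also allows the Week 52/Baseline visit to be up to 10 days late.

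On the relapse date, SAP 7.3.1.2 says: "The time of first relapse is the date of the earliest menstrual bleeding days within the first FP collection visit window" with a volume of at least 80 mL. For time to relapse, SAP 7.4.1.1 says: "The corresponding menstruation start date will be considered as the event date".

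**The concern.** A woman whose relapse begins on Day 370 was relapse-free on Day 365. A Kaplan-Meier estimate at Day 365 should treat her as event-free and censored there. Under the rule as written she is a failure at Day 365, which pulls the estimate down.

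The rule also makes the result depend on scheduling. Two women who both begin to bleed heavily on Day 370 are treated differently if one had her last visit on Day 360 (censored) and the other on Day 375 (event). An alpha-controlled endpoint should have a horizon that visit timing does not stretch.

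**Working it through.** **1. The plan's own figure.** SAP 2.2 states that "the study would have at least 90% power to detect a difference of 20% or greater", with rates of 40% and 60%, 1:1 allocation, 360 patients, 20% dropout and two-sided alpha 0.05. After dropout there are 360 × 0.8 / 2 = 144 per arm. Power = Φ[(0.20 − 1.96·√(2·0.5·0.5/144)) / √((0.24 + 0.24)/144)] = Φ[(0.20 − 0.1155)/0.0577] = Φ(1.46) = 92.8%. The stated figure is reproduced and is not in dispute. The planning rates are used below only to size the effect.

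**2. When can the last visit fall?** Let the baseline visit be k days late (0 to 10) and the Week 104 visit j days after the anniversary (0 to 10).
- The baseline visit is on parent-study Day 365 + k, so study Day 1 is parent-study Day 366 + k.
- The anniversary of parent-study Day 1 is parent-study Day 731, so the last visit is on parent-study Day 731 + j.
- In study days: (731 + j) − (366 + k) + 1 = 366 + j − k, which runs from Day 356 to Day 376.

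A woman with an on-time baseline visit (k = 0) therefore has every compliant Week 104 visit after Day 365.

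**3. Upper bound.** Assume a constant hazard, λ = −ln S(169)/169.
- Relugolix: λ = 0.5108/169 = 0.00302 per day.
- Placebo: λ = 0.9163/169 = 0.00542 per day.

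If every last visit were on Day 376, the rule would report S(376) in place of S(365):

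| Arm | S(365) | S(376) | Shift (points) |
|---|---|---|---|
| Relugolix | 33.2% | 32.1% | 1.1 |
| Placebo | 13.8% | 13.0% | 0.8 |
| Difference | 19.4 | 19.1 | 0.3 |

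**4. With visits spread over the window.** A simulation used 180 per arm, the hazards above, 20% dropout uniform over Days 1 to 365, j and k independent and uniform on 0 to 10, and 2,000 replicates. It compared Kaplan-Meier estimates at Day 365:

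| Arm | SAP rule | Censored at Day 365 | Shift (points) |
|---|---|---|---|
| Relugolix | 32.7% | 33.1% | 0.4 |
| Placebo | 13.4% | 13.7% | 0.3 |
| Difference | 19.3 | 19.4 | 0.1 |

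About 0.3 relapses per arm fall after Day 365. The Day 169 estimates are identical under both rules (60.0% and 40.0%).

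**5. Other rates.** With 80% and 15% at Week 76, the arms fall by 0.31 points (61.73% to 61.42%) and 0.06 points (1.67% to 1.61%), so the difference shrinks by 0.25 points. With 60% in both arms, each falls by 0.36 points, so the rule creates no difference where there is none, given equal visit timing in the arms.

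**The case against.** The best defence is that Day 365 is a nominal target. SAP Table 2 assigns monthly assessments after that day to Week 104, so placing the last collection on its nominal day is a recognisable convention. Censoring would also classify a woman with at least 80 mL at her Week 104 collection as relapse-free at Week 104 if her bleeding began on Day 366 or later. This stands as a real, small cost of the fix. It does not rescue the rule, because the estimate is defined at Day 365 and the convention leaves follow-up dependent on visit timing. If the sponsor wants the whole Week 104 collection to count, the SAP should say so as the definition.

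It is also fair to say that the effect is small and, at the planning rates, slightly unfavourable to relugolix. Both stand.

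A reader might infer several stronger points that the documents do not support:
- **That the primary is affected.** It is not. The curve continues past Day 169, so no end-of-curve rule is needed there, and its absence is not an inconsistency.
- **That relapses can begin up to 17 days late** (10 days plus the 7-day collection extension). The extension in SAP 7.3.2.3 covers women already bleeding at the visit. Relapse is dated at the start of bleeding, so the extension adds no later onsets.
- **That the SAP gives two contradictory relapse dates.** In ordinary cyclic bleeding within one window, the earliest menstrual bleeding day is the menstruation start date. The dates could part company with irregular bleeding, or if menses began before the window opened, but the documents give no basis for how often or by how much. A one-day shift in every patient would move the Day 169 rates by λ·S(169) = 0.18 points (relugolix) and 0.22 points (placebo).
- **That the SAP promises time to relapse and the primary from the same curves.** That statement concerns the Week 104 rate. For time to relapse, SAP 7.4.1.1 takes over only the censoring rules.

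**Conclusion.** The concern holds for the Day 365 rule. As written, it biases the Week 104 sustained responder rates slightly downward. At the planning rates the size is about 0.3 to 0.4 points per arm (at most about 1.1) and about 0.1 point on the treatment difference (at most about 0.3). No reversed conclusion has been shown. The case for acting is that an alpha-controlled rate should not depend on how late the last visit is, and that the correction is simple.

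The sizes rest on a constant hazard, uniform visit timing within the protocol windows and uniform dropout. The documents supply none of these. Only the range of compliant visit days comes from them. The difference in wording between 7.3.1.2 and 7.4.1.1 is a matter for clarification, not a separate defect.

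**What to change.** In SAP 7.3.1.2, replace the sentence on times after Day 365 with: *Patients whose first relapse or last available collection is after Day 365 are censored, event-free, at Day 365.* Repeat this in Table 8.

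The cost is one sentence and one derivation rule, settled before unblinding. A relapse found at a late Week 104 collection with onset after Day 365 would no longer count in the Week 104 rate. A sensitivity analysis that counts the whole Week 104 collection can report it.

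As a minor clarification, 7.4.1.1 should cross-refer to the relapse date in 7.3.1.2, so that time to relapse and both sustained responder rates use one event date. A date for the individual bleeding episode that reached 80 mL would not always be derivable, because SAP 7.3.2.4 sums volume over the collection interval.

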7.3.2. Definitions Related to Menstrual Blood Loss for Each Feminine Product Collection Interval

The data sources that will be used to support derivation of responder status for each FP collection interval include:

- Menstrual blood loss volume determined by the alkaline hematin method;
- Daily patient report of bleeding (yes/no) and use of FP (yes/no) captured in the paper patient diary;
- The status of FP collection return (yes/no) recorded on the eCRF page at each visit with specific reasons captured when no product collection was returned.

The total MBL volume is reported from the analysis of FP returned for each collection interval. An inventory of days (with dates) for which FP was collected and returned is also available. This inventory is aligned with patients' reports of bleeding and FP use in the paper patient diary. The status of FP collection return, and specifically the reason for non-return of FP reported on the Feminine Product Collection eCRF page is used to support derivation of responder status (see Section 7.3.3 for details).

7.3.2.1. Menstrual Blood Loss Volume

All returned FPs (validated, validated but unauthorized, or unvalidated products) collected at each visit will be analyzed by the alkaline hematin method to obtain the MBL volume. The MBL volume measured over each FP collection interval will be used to determine responder status at that visit (see details below). The vendor, KCAS, reports when unauthorized FPs (products not dispensed for use in the trial) have been returned. KCAS also reports whether the unauthorized products have previously been validated for their analysis. The report details MBL volumes for authorized, unauthorized but validated, and unauthorized and unvalidated products.

7.3.2.2. Week 52/Baseline Menstrual Blood Loss Volume

Week 52/Baseline MBL volume is defined as the last available MBL volume which was collected on or after the Week 44 in MVT-601-3003 and prior to the date of the first dose of randomized withdrawal study drug as assessed by the alkaline hematin method. If a patient did not return any FPs and reported amenorrhea, Week 52/Baseline MBL volume is set to 0 mL.

Although the responder status used to determine the patient's eligibility for this study is based on Week 48 data (or Week 44 data if Week 48 data were not available at the time when eligibility was being assessed) in MVT-601-3003, the Week 52/Baseline MBL volume defined above will be used to establish the patient's baseline for evaluation of menstrual blood loss of this study.

In addition, baseline MBL volume for the retreatment period is defined as the highest value prior to the first dose of the retreatment drug. This definition will be used for retreatment period related summaries.

7.3.2.3. Feminine Product Collection Interval

The FP collection interval at each visit is driven by types of bleeding patterns experienced by the patients, as described below:

- For patients who continue to have cyclic bleeding, the length of the interval depends on the duration of the patient's natural cycle;
- Patients who report irregular, non-cyclic bleeding are instructed to collect and return all FP used between study visits, up to 35 days, as per the schedule of events;
- For patients who report amenorrhea on the Feminine Product Collection eCRF page, an interval of last 35 days of treatment will be reviewed to ensure that reported amenorrhea is not due to incomplete collection.

For patients who are in the midst of an episode of cyclic bleeding at the time of the FP collection visit (or the last visit in the randomized treatment period which is prior to Week 104), the visit window may be extended up to 7 days after Week 104 visit (or last visit) to ensure patients return all used FPs over that bleeding episode.

Per protocol, all used FPs are to be collected at each visit and returned for analysis using the alkaline hematin method. For patients who continue to have menstrual bleeding, study visits are timed such that the FPs used in the entire menstrual bleeding cycle are collected in one container provided at each visit.

7.3.2.4. Menstrual Blood Loss Volume for Each Feminine Product Collection Interval

Menstrual blood loss volume for each FP collection interval is defined as the MBL volume obtained from the FP returned over the FP collection interval (or the FP collection interval between the two consecutive visits during the randomized treatment period which is prior to Week 104). Sum of MBLs from multiple FP collection kegs (if any) within the same FP collection interval will be used as the total MBL for that visit. The total MBL volume over each FP collection interval will be used to derive the responder status at that visit.

If a patient did not return FP over the FP collection interval prior to retreatment and reported amenorrhea on the Feminine Product Return eCRF page, she will be considered as amenorrheic and her MBL volume will be assigned as 0 mL.

If a patient did not return FP over the FP collection interval prior to retreatment and reported spotting on the Feminine Product Return eCRF page, her MBL volume will be assigned as <5 mL.

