Patients were to be asked to collect FPs for alkaline hematin analysis and to return them at each visit until the analysis confirmed the return of heavy menstrual bleeding (defined as menstrual blood loss volume of ≥ 80 mL). The patients were then to be offered re-treatment with open-label relugolix +E2/NETA with the onset of the next menses. They were to continue collection of FPs for alkaline hematin analysis until two consecutive analyses confirmed resolution of heavy menstrual bleeding (menstrual blood loss of < 80 mL). Patients who experienced a return of heavy menstrual bleeding (or terminate early because they have a return of heavy menstrual bleeding) but who decline retreatment with open-label study drug were to complete an Early Termination visit and a 30-day Safety Follow-Up visit.

At the Week 104/Early Termination visit, all other patients were to have an assessment of bone mineral density (BMD) via dual-energy x-ray absorptiometry (DXA). Patients were to complete the bleeding diary daily, including compliance with study drug, vaginal bleeding, and use of FPs.

If a patient enrolls directly into another relugolix clinical study upon completion of the Week 104/Early Termination visit, then the Safety Follow-Up visit and the follow-up procedures performed under this protocol may be waived.

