7.1.1. Analyses for Categorical Data

Qualitative variables will be summarized by frequency counts and percentages. Unless otherwise specified, the calculation of proportions will include the missing category. Therefore, counts of missing observations will be included in the denominator and presented as a separate category.

For efficacy endpoints evaluating proportions descriptive statistics (point estimates and corresponding 95% CIs) will be provided by treatment group and visit as appropriate.

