7.3.2.5. Feminine Product Return Rate by Visit

To quantify degree of compliance with FP collection during the randomized treatment period, the FPRR will be calculated based on the inventory of FP returned by day (dates) provided by the vendor, KCAS, the reason why the FP was not collected from the Feminine Product Collection eCFR page, and responses to the paper patient diary questions regarding bleeding experience and the use of FP obtained for the corresponding diary window (see [Table 6](#)). Specifically:

- For those who returned FP at a FP collection visit, the FPRR was calculated as the observed number of days with returned FPs (based on the inventory of FP received by KCAS) divided by the expected number of days with bleeding and use of product as reported on the patient's paper diary within the FP collection interval (as defined above).

$$\text{FPRR} = \frac{\text{observed (No. of days with returned FP [per KCAS])}}{\text{expected (No. of days reported bleeding and use of FP [per Diary])}} \times 100$$

- For those who did not return any FPs:
 - If the reason was "Amenorrheic" or "Patient only had Spotting that did not require the use of Sanitary Products" on the eCRF, their FPRR will be set to 100% because the lack of menstruation obviates the need for FP collection.
 - If the reason was "Patient failed to collect Used Products per Protocol" on the eCRF, their FPRR was set to 0.
 - If the reason was "Retreatment Visit; No Product Collection Required" or "Successful Retreatment; No Product Collection Required" on the eCRF, their FPRR was set to 0.
 - If the reason is "Other", their FPRR was set to 0.

The texts specified for reason "Other" will be reviewed by the medical team to identify those which belong to any pre-defined reasons listed in the first three bullets above and the reason will thus be treated accordingly.

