7.3.3. Identifying Responder Status and Incomplete Feminine Product Collection at Each Visit

For each schedule visit, responder (MBL volume < 80 mL) status and incomplete FP collection will be identified for each patient by checking compliance with FP collection against the patient's paper diary, as measured by FPRR, and reasons for no FP collection (as displayed in Table 9).

Table 9: Identifying Incomplete Feminine Product Collection and Derivation of Responder Status at Each Visit During Randomized Treatment Period

FP Collection (Yes/No)	Reason for No FP Collection (CRF page)	Observed MBL Volume	FPRR	Incomplete FP collection	Responder Status
Yes	N/A	< 80 mL	>80-100%	Complete	Yes
	N/A	≥ 80 mL	N/A	N/A	No
	N/A	< 80 mL	≤ 80%	Incomplete, Not acceptable	Missing
No	Amenorrheic	Set as 0 mL	100%	Complete	Yes
	Patient only had spotting that did not require the use of sanitary products	Set as 4.99 mL	100%	Complete	Yes
	Patient failed to collect used products per protocol	Missing	0%	Incomplete	Missing
	Retreatment visit; No product collection required	N/A	N/A	N/A	N/A
	Successful retreatment; No product collection required	N/A	N/A	N/A	N/A
	Other	Missing	0%	Incomplete	Missing

Abbreviations: FP = feminine product; FPRR = feminine product return rate; MBL = menstrual blood loss; N/A = not available.

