7.4.2. Other Secondary Endpoints

7.4.2.1. Proportion of Patients Who Responded to Retreatment During the Retreatment Period

Proportion of patients who responded (MBL volume of < 80 mL) to retreatment with open-label relugolix 40 mg +E2/NETA during the retreatment period among placebo patients whose MBL volume had returned to \geq 80 mL during the randomized treatment period will be summarized descriptively. The point estimate and its corresponding 95% CIs will be provided.

The change and percent change in MBL volume from retreatment initiation will also be summarized descriptively as a continuous variable every 4 weeks after retreatment initiation during the retreatment period.

7.4.2.2. Change and Percent Change from Week 52/Baseline in Menstrual Blood Loss Volume During the Randomized Treatment Period

The change (for all patients) and percent change (for patients who did not have amenorrhea at baseline) in MBL volume from Week 52/baseline will be summarized descriptively as a continuous variable at each visit during the randomized treatment period including Week 76 and Week 104 visits. Observed MBL volume for each timepoint will be used to calculate change and percent change from Week 52/Baseline. In addition, the change and percent change in MBL volume from Week 52/baseline will also be summarized descriptively as a continuous variable at each visit during the cumulative treatment period.

For change and percent change in MBL volume, mixed-effects model will not be used to derive LS means (and 95% CIs) due to skewed distribution of MBL volumes (majority of patients experiencing amenorrhea with MBL volume set as 0 mL at baseline). Descriptive statistics (medians and simple means) will be provided for each treatment group.

Categorical summary of change in MBL volume will be provided by grouping patients into three categories: who had increase, no change, and decrease in MBL volume from Week 52/Baseline over time by visit for cumulative treatment period. A figure will also be provided to display the percentages for each category by treatment group every 12 weeks from Week 52/Baseline up to Week 104.

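### The amenorrhea, spotting and incomplete-return rules stop at retreatment, so the retreatment-response endpoint gives an amenorrheic woman no value and accepts partial returns below 80 mL

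*SAP*

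**What the plan says.** SAP 7.3.2.4 assigns a volume to women who hand in no products. A patient who "did not return FP over the FP collection interval prior to retreatment and reported amenorrhea" is given 0 mL. One who "did not return FP over the FP collection interval prior to retreatment and reported spotting" is given less than 5 mL (4.99 mL in Table 9). Both sentences carry the same time limit.

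SAP 7.3.2.5 introduces the FPRR with its own limit: "To quantify degree of compliance with FP collection during the randomized treatment period, the FPRR will be calculated". Table 9 in SAP 7.3.3 sets responder status to missing when the volume is below 80 mL but FPRR is 80% or less. Its title ends "Derivation of Responder Status at Each Visit During Randomized Treatment Period".

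The retreatment endpoint in SAP 7.4.2.1 is the "Proportion of patients who responded (MBL volume of < 80 mL) to retreatment with open-label relugolix 40 mg +E2/NETA during the retreatment period". It is restricted to relapsed women from the placebo arm. That section adds no rule for amenorrhea, spotting or incomplete return, and names no visit. It also summarizes the change in volume from retreatment initiation every 4 weeks.

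The defaults differ. SAP 4.1 does not impute missing efficacy data unless otherwise specified. For proportions, SAP 7.1.1 says "counts of missing observations will be included in the denominator and presented as a separate category". For by-visit observed data, SAP 4.1 uses non-missing denominators, and SAP 4.4.1 keeps only observed records. Protocol 9.3.2.1 places the retreatment proportion at the end of the retreatment period and leaves derivations and missing data to the SAP.

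**The concern.** Recapture of response after an interruption is a stated secondary objective and part of the design rationale (Protocol 4.2). It has no concurrent control, so its credibility rests on how a responder is defined. The SAP builds that definition carefully for the randomized period, then limits the supporting rules to that period. After restart, the best possible outcome (no bleeding, nothing to return) produces no data point. An incomplete return that would have been rejected earlier is accepted. The two errors pull the reported rate in opposite directions.

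The same gap reaches the volume change after restart, which is computed only in women with measured returns, and the cumulative-period summaries of volume below 80 mL in SAP 7.4.1.2 and 7.4.2.2.

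**Working it through.** The documents state no expected rate or precision for this endpoint, so there is no planned figure to reproduce. The check is one of scope, followed by arithmetic on labelled assumptions.

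**Scope of each rule**

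| Rule | Source | Before retreatment | After restart |
|---|---|---|---|
| No return, amenorrhea: 0 mL, responder | SAP 7.3.2.4, Table 9 | applies | not covered |
| No return, spotting: <5 mL, responder | SAP 7.3.2.4, Table 9 | applies | not covered |
| <80 mL with FPRR ≤80%: status missing | SAP 7.3.2.5, Table 9 | applies | not covered |
| Missing efficacy data not imputed | SAP 4.1 | applies | applies |
| Retreatment response: volume <80 mL | SAP 7.4.2.1 | – | sole criterion |

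**Amenorrhea.** Protocol 6.2 does not require collection of the bleed at which retreatment starts. A woman who does not bleed again therefore never has a measured volume after restart, and no rule assigns one.

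**Partial return.** FPRR = days with returned product ÷ diary days with bleeding and product use × 100. An invented case: products from 1 of 5 bleeding days, measuring 20 mL, give FPRR = 1/5 = 20%. Table 9 would call this missing; 7.4.2.1 as written calls it a response.

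**Simple size.** Suppose every retreated woman responds and a fraction *a* is amenorrheic at every interval after restart (assumption).

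- Missing in the denominator (7.1.1): rate = 1 − *a*. For *a* = 0.3 it is 70%; for *a* = 0.5 it is 50%.
- Observed data (4.1, 4.4.1): rate = (1 − *a*)/(1 − *a*) = 100%.

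**Fuller illustration.** Take N = 108, from half of 360 (180) × (1 − 0.40), using the placebo responder rate in SAP 2.2 only to set a scale. Assume 10% still at 80 mL or more (11 women), 50% amenorrheic with no return (54), 5% partial returns below 80 mL (5), and the rest complete returns below 80 mL: 108 − 11 − 54 − 5 = 38. Intervals are exact 95% CIs.

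| Reading | Missing in denominator | Observed data |
|---|---|---|
| As written (38 + 5 = 43 responders) | 43/108 = 39.8% (30.5 to 49.7) | 43/(108 − 54) = 43/54 = 79.6% (66.5 to 89.4) |
| Rules extended (54 + 38 = 92 responders) | 92/108 = 85.2% (77.1 to 91.3) | 92/(108 − 5) = 92/103 = 89.3% (81.7 to 94.5) |

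Moving the amenorrheic share from 30% to 70% takes the as-written rate from 65/108 = 60.2% to 21/108 = 19.4% with missing in the denominator, and from 65/76 = 85.5% to 21/32 = 65.6% on observed data. The extended-rule rate does not depend on that share. Once some women fail retreatment, the observed-data basis is also pulled down, because it drops amenorrheic responders and keeps every failure.

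**The case against.** The best counter-argument is that the SAP meant the rules to run on. The sentence introducing Table 9 refers to every scheduled visit with no period limit. Both 7.3.2.5 and Table 9 include a reason for no collection after successful retreatment, which can arise only after restart. SAP 7.4.2.2 plans shift tables with a 0 mL category for the cumulative period, and below-quantification results are set just under the limit (SAP 4.1), so that category appears to need assigned amenorrhea values. These are fair signs of wider intent, and they make a deliberate exclusion of amenorrheic women unlikely. They do not override the explicit time limit in 7.3.2.4. The successful-retreatment reason is itself inconsistent: FPRR is 0 in 7.3.2.5 and not applicable in Table 9.

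Three limits on the point stand:

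- The amenorrheic share after restart is unknown. The SAP's remark that most women had 0 mL describes Week 52/Baseline in selected responders, not women who relapsed on placebo and restarted.
- If any volume below 80 mL during retreatment suffices, a woman with one measured collection has a value even if she is amenorrheic later.
- The fall to 50% to 70% occurs only on the missing-in-denominator basis.

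A reader might also infer that response should require two consecutive results below 80 mL, since SAP 2.1 uses that pattern to confirm resolution. The documents do not support this. It is a rule for ending product collection; Protocol sections 3 and 9.3.2 define retreatment response as a volume below 80 mL. Requiring two results would also leave women who restart late unconfirmed. Nor do the documents say that one reading at any time suffices: the SAP names no visit, and the protocol points to the end of the retreatment period.

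**Conclusion.** The point holds as a scope defect with a real effect on one secondary endpoint. The consequences follow from the stated time limits combined with the no-imputation default; the SAP does not spell them out. A retreated amenorrheic woman with no return has no volume, and whether she counts against response or disappears is unsettled. A partial return below 80 mL counts as response.

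The effect could be nil or tens of percentage points: in the all-respond scenario with 30% to 50% amenorrheic throughout, the reported rate is 70% to 50% on one denominator and 100% on the other. The inflation from partial returns cannot be sized from the documents.

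It would be wrong to read this as a threat to the trial's main conclusions. The endpoint is summarized descriptively and lies outside the fixed testing sequence, so the primary and key secondary tests are untouched.

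**What to change.** Before unblinding:

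1. In SAP 7.3.2.4, delete the words that restrict the 0 mL and <5 mL assignments to intervals before retreatment.
2. Apply the amenorrhea, spotting, failed-to-collect and FPRR ≤80% rows of Table 9 to retreatment-period intervals while collection is still required. Amend the scope wording of 7.3.2.5 and the table title to match. The uncollected bleed at restart should not enter the expected days in the FPRR denominator.
3. Treat the retreatment-visit and successful-retreatment reasons as not applicable in both 7.3.2.5 (now FPRR 0) and Table 9.
4. In 7.4.2.1, state the denominator and the time point, reconciled with the protocol's end of the retreatment period. Women whose collection stopped for successful retreatment keep their last evaluable status.
5. Keep the protocol criterion of a volume below 80 mL.

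The cost is SAP wording and some programming. The eCRF reasons, diary entries and laboratory inventory are already collected. Some partial returns that would have counted as responses will become missing, so the number of missing statuses should be shown beside the rate.
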